9.2.2 AE and Device Deficiency Documentation

All AEs will be monitored for all participants, from the time of signing consent through to the final study visit. All AEs, including SAEs, must be detailed in the source documents and reported in a timely manner to the Sponsor by completing an AE page in the CRF. Each unique event must be documented separately.

AEs can be based upon subject report, questionnaires, medical reports or other medical examinations. AEs should be documented in terms of a medical diagnosis. When this is not possible, the AE should be documented in terms of signs and/or symptoms observed by the Investigator or reported by the subject at each study visit. For each medical diagnosis or sign and/or symptoms the Investigator will provide information on dates (onset/resolution), severity, relationship to the medical device, action(s) taken and outcome.

Any AEs should be followed until the event is resolved (with or without sequelae). If an event is ongoing at the time of study completion or termination, the participant will be followed until resolution or Investigator determination that the subject's condition is stable. Documentation of stabilization must be recorded in the participant's source documents. If the Investigator learns of any SAE at any time after a participant has been discharged from the study, and he/she considers

the event reasonably related to the study device and/or study procedure, the Investigator will record the occurrence in the subject's source documents and promptly notify the Sponsor.

If adverse events occur, the first concern will be the safety of the subject. Appropriate medical intervention will be made as soon as possible. Treatment of any AEs is at the sole discretion of the Investigator and according to current good medical practice. Any medication administered for the treatment of an AE should be recorded in the CRF.

All device deficiencies, including serious incidents (a device deficiency that might have led to a SADE if a) suitable action had not been taken, b) intervention had not been made, c) if circumstances had been less fortunate), shall be documented throughout the study in the source documents and appropriately reported on a device deficiency page of the CRF.

9.2.3 Reporting of events

AEs must be reported to the Sponsor or designee by the Investigator immediately but no later than 3 calendar days after investigation site study personnel's awareness of the event of the following:

- i. SAE,
- ii. SADE,
- iii. SAPE,
- iv. USADE,
- v. Device deficiency (DD) that might have led to a serious adverse event if appropriate action had not been taken, intervention had not occurred, or circumstances had been less fortunate,
- vi. New findings in relation to any event mentioned to in points i) to v).

Notification should be made by completion of the AE form in the CRF and by contacting by phone and/or by email the sponsor or designee.

As additional information becomes available, the event should be updated in the CRF and provided to the sponsor or designee.

Non-serious AEs should be reported at the next routine contact.

9.2.4 AE and DD information and Classification

The Investigator will classify each AE and DD according to the Adverse Event Form. If the AE is serious or the Investigator feels that the device contributed in any way to the AE, the Investigator must report the event to the Sponsor and the EC, if applicable, as per above. It is the Investigators responsibility to assess the intensity of, as well as determine the causality and potential relationship of the event to the study device or procedure. The Sponsor may ask for further clarification and information to support the AE classification. If sufficient questions arise, the Sponsor may ask the DSMB to adjudicate the classification. The Sponsor may assess the potential relationship to the device or procedure differently than the Investigator; in that case, both conclusions will be collected and reported, if applicable.

The following information will be collected for any event occurring during the course of this investigation:

- Date of event onset,

- In case of SAE, SADE, SAPE, USADE, DD that might have led to a SAE in other circumstances: classification of the event (death - life-threatening illness or injury - permanent impairment/chronic disease – hospitalization - medical or surgical intervention - fetal distress, fetal death or congenital physical or mental or birth defect)
- Description of the event
- Action / treatment / patient outcome
- Intensity of the event (mild, moderate, severe)
- Relationship to procedure (not related, possible, definite)
- Relationship to study device (not related, possible, definite)
- Event status (resolved, resolved with sequelae, ongoing, death)

9.2.5 Emergency contact details for reporting reportable events

Sponsor and designee contact details for reporting reportable events are detailed in the study contacts at the beginning of the present clinical investigation plan.

9.2.6 Safety Monitoring

Safety oversight will be under the direction of a Data Safety Monitoring Board (DSMB). The DSMB shall be independent from the study conduct and free of conflict of interest, or measures should be in place to minimize perceived conflict of interest. The DSMB will operate under the rules of an approved charter that will be written by the sponsor and reviewed and approved by the DSMB.

The DSMB will be responsible for initial review of all events reported as serious. Further information may be sought from the investigational site. Events will be reviewed to check relatedness and seriousness to enable appropriate reporting to the ethics and regulatory bodies, as well as take any appropriate action with regards to study continuation.

The DSMB will include at least two physicians who have experience with hemodialysis and vascular access and one statistician.

9.2.7 Definition of Adverse Events (AE)

Adverse event means any untoward medical occurrence associated with the use of an intervention in humans, whether or not considered intervention-related.

Note: Pain and/or bleeding that is to be expected due to hemodialysis during the intervention are not considered untoward events and should not be recorded as adverse events. Likewise, minimal bruising, pain, and/or bleeding in the days following the procedure shall not be considered untoward and not considered an AE. In contrast, any pain, bruising, or bleeding that is considered by the clinician to be unusual in magnitude or duration shall be considered an AE.

9.2.8 Definition of Serious Adverse Events (SAE)

An adverse event (AE) or suspected adverse reaction is considered "serious" if, in the view of either the investigator or sponsor, it results in any of the following outcomes: death, a life-threatening adverse event, inpatient hospitalization or prolongation of existing hospitalization, a persistent or significant incapacity or substantial disruption of the ability to conduct normal life functions, or a congenital anomaly/birth defect. Important medical events that may not result in death, be life-threatening, or require hospitalization may be considered serious when, based upon appropriate medical judgment, they may jeopardize the participant and may require medical or

surgical intervention to prevent one of the outcomes listed in this definition. Examples of such medical events include allergic bronchospasm requiring intensive treatment in an emergency room or at home, blood dyscrasias or convulsions that do not result in inpatient hospitalization, or the development of drug dependency or drug abuse.

9.2.9 Classification of an Adverse Event

9.2.10 Severity of Event

The following guidelines will be used to describe severity of AEs:

- **Mild** – Events require minimal or no treatment and do not interfere with the participant's daily activities. For cannulation injuries, An injury that may result in bleeding, infiltration, and swelling that may be treated with conservative measures such as ice and rest for 1 to 2 days; cannulation can be reattempted for the next dialysis session. The access should be successfully recannulated with 2 needles in ≤ 7 days.² Even a minor cannulation injury may require the use of a temporary catheter.
- **Moderate** – Events result in a low level of inconvenience or concern with the therapeutic measures. Moderate events may cause some interference with functioning. For cannulation injuries, an injury that results in significant bleeding, infiltration, and swelling that requires recovery for >7 days.
- **Severe** – Events interrupt a participant's usual daily activity and may require systemic drug therapy or other treatment. Severe events are usually potentially life-threatening or incapacitating. Of note, the term "severe" does not necessarily equate to "serious". For cannulation injuries, an injury that results in significant bleeding complications that requires one of the following: blood transfusion, emergency department visit, hospitalization, or endovascular or surgical intervention.

9.2.11 Relationship to Study Intervention

All adverse events (AEs) must have their relationship to study device/procedure assessed by the clinician who examines and evaluates the participant based on temporal relationship and his/her clinical judgment. The degree of certainty about causality will be graded using the categories below. In a clinical trial, the study product must always be suspect.

- **Definitely Related** – The AE is known to occur with the study device/procedure, or it is known that the study device/procedure caused the AE.
- **Possibly Related** – The AE could have occurred due to the study device/procedure, there is a reasonable possibility that the study device/procedure caused the AE, or there is a temporal relationship between the study device/procedure and event. Reasonable possibility means that there is evidence to suggest a causal relationship between the study device/procedure and the AE.
- **Not Related** – There is not a reasonable possibility that the administration of the study device/procedure caused the event, there is no temporal relationship between the study device/procedure and event onset, or an alternate etiology has been established.

9.2.12 Expectedness

The Data Safety Monitoring Board (DSMB) will be responsible for determining whether an adverse event (AE) is expected or unexpected. An AE will be considered unexpected if the nature, severity, or frequency of the event is not consistent with the risk information previously described for the study intervention.

9.2.13 Time Period and Frequency for Event Assessment and Follow-Up

The occurrence of an adverse event (AE) or serious adverse event (SAE) may come to the attention of study personnel during study visits and interviews of a study participant presenting for medical care, or upon review by a study monitor.

All AEs including local and systemic reactions not meeting the criteria for SAEs will be captured on the appropriate case report form (CRF). Information to be collected includes event description, time of onset, clinician's assessment of severity, relationship to study product (assessed only by those with the training and authority to make a diagnosis), and time of resolution/stabilization of the event. All AEs occurring while on study must be documented appropriately regardless of relationship. All AEs will be followed to adequate resolution.

Any medical condition that is present at the time that the participant is screened will be considered as baseline and not reported as an AE. However, if the study participant's condition deteriorates at any time during the study, it will be recorded as an AE.

Changes in the severity of an AE will be documented to allow an assessment of the duration of the event at each level of severity to be performed. AEs characterized as intermittent require documentation of onset and duration of each episode.

Study clinicians will record all reportable events with start dates occurring any time after informed consent is obtained until 7 days after the last day of study participation. At each study visit, the investigator will inquire about the occurrence of AEs since the last visit. Events will be followed for outcome information until resolution or stabilization.

10 Statistical Considerations

10.1 Statistical Hypotheses

10.1.1 Sample Size

The sample size was determined to compare the rate of successful treatments between hemodialysis sessions with the test needle compared to the control needle.

The hypothesis test for the primary performance measure is defined as follows:

$$H_0: p_T - p_C \leq -\delta$$

$$H_1: p_T - p_C > -\delta$$

where p_T is the probability of a successful hemodialysis treatment session with the V Needle (test), p_C is the probability of a successful hemodialysis treatment session with a commercially available device (control), and δ is the non-inferiority margin.

This sample size estimation is based on the following assumptions:

- The expected success rate for both devices is 98%
- The expected difference between the test and control treatment groups is 0%
- There is a test-to-control sampling ratio of 2:1
- A non-inferiority margin of 8% ($\delta = 0.08$)
- Use of a one-sided Farrington-Manning Score Test with 85% power and at a one-sided 2.5% significance level

Based on these assumptions, a statistically powered sample size of 87 test (V Needle) sessions is required for the primary endpoint^{4,5}.

The total sample size is therefore determined to be 108 test sessions with 18 subjects required to account for 20% attrition and/or any of the 6 V Needle sessions being missed.

The primary performance analysis will test the non-inferiority hypothesis as a difference of proportions between the test and control groups using a one-sided Farrington-Manning Score Test at a significance level of $\alpha=0.025$.

Additionally, the primary performance measure will be analyzed on the subject-level (utilizing a non-inferiority margin of 0.05) by testing the difference in mean success rates per subject across treatment groups using a one-sided paired t-test at a significance level of $\alpha=0.025$.

10.1.2 Primary Hypothesis

The primary performance goal for this study is that the Hemotek device will provide successful hemodialysis treatment at a rate non-inferior to that of the commercially available devices. The rate of successful treatment will be computed as the number of successful session completions of V Needle, as determined by the clinician, divided by the total number of sessions attempted.

To determine whether a dialysis session was successful, clinicians will be asked “Was dialysis session incomplete because of a vascular access issue?” If the answer is “No,” this indicates that the dialysis session completed successfully or was stopped for reasons that were not related to the vascular access (e.g., patient illness, etc.).

The null hypothesis is that the difference between the rates of successfully completed hemodialysis sessions for the test and control groups is less than or equal to the non-inferiority margin (indicating inferior success rate). Rejection of the null hypothesis indicates the observed data supports the alternative hypothesis that the difference between the rates of successfully completed hemodialysis session for the test and control groups is at least the non-inferiority margin (indicating non-inferior success rate).

The hypothesis test for the primary analysis are defined as follows:

$$H_0: p_T - p_C \leq -\delta$$

$$H_1: p_T - p_C > -\delta$$

where p_T is the probability of a successful hemodialysis treatment session with the V Needle (test), p_C is the probability of a successful hemodialysis treatment session with a commercially available device (control), and δ is the non-inferiority margin.

⁴ Chow, S.C., Shao, J., and Wang, H. 2008. Sample Size Calculations in Clinical Research, Second Edition. Chapman & Hall/CRC. Boca Raton, Florida.

⁵ Farrington, C. P. and Manning, G. 1990. 'Test Statistics and Sample Size Formulae for Comparative Binomial Trials with Null Hypothesis of Non-Zero Risk Difference or Non-Unity Relative Risk.' Statistics in Medicine, Vol. 9, pages 1447-1454.

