3.3 Risk/Benefit Assessment

3.3.1 Known Potential Risks

Risks related to the study and/or device are expected to be the same as those risks for patients undergoing hemodialysis. Due to the design of the V Needle, very slight increases in certain risks are potentially possible but are not expected.

The potential risks specifically associated with the V Needle are as follows:

- Improper needle function, leading to machine false alarms or changes to dialysis blood flow rate or pressure
- Difficulty inserting the needle into the veins (cannulation)
- Slightly increased risk of blood loss and/or air embolism

The risks associated with all AV fistula sets are as follows:

- Air in the tubing/blood vessels, which could result in blockage and reduced blood flow in that vessel or other vessels in the body
- Allergic responses to the device materials, such as swelling, itchiness, or inflammation of the skin
- Small particles released into the blood vessels, which could result in blockage and reduced blood flow in that vessel or other vessels in the body
- Improper function of the device, leading to delay in therapy
- Infection
- Breakdown of blood cells due to unstable blood flow (hemolysis), which can lead to fatigue, dizziness, and headaches
- Blood loss
- Blood leaks into surrounding tissue, leading to swelling and/or pain (infiltration, when the needle tip is placed into the body but not directly into the blood vessel)
- Injury from sharp needle

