4.3 PRIMARY PERFORMANCE MEASURES

Percentage of successful hemodialysis sessions with the Hemotek device.

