5.1 Overall Design

This study is a prospective, multi-center, single-arm study with subjects acting as their own control designed to confirm the safety, performance, and usability of the V Needle, a new safety needle for use during in-clinic hemodialysis that is designed to automatically generate a partial occlusion of the internal fluid path and trigger the hemodialysis machine to alarm and shut off if a complete dislodgement of the venous needle from the arm inadvertently occurs.

For the first three (3) control sessions, consenting subjects will undergo usual hemodialysis sessions with a commercially available device. For the remaining six (6) test sessions, subjects will be cannulated with a V Needle in place of a usual venous line AV fistula set.

The hemodialysis sessions will be conducted in the clinic. Subjects will be observed by a clinician for the duration of each session. Clinicians will monitor the session for any abnormal disruptions, therapy interruptions, and/or adverse events, including hemolysis, due to V Needle presence. All machine blood alarms, therapy interruptions, and/or partial or complete needle dislodgements will be recorded and immediately corrected. Clinicians will be responsible for identifying adverse events as they occur and will activate established facility emergency response plans if necessary. A clinician will perform cannulation.

Cannulation site and surrounding tissue will be examined by the nurse and assessed for any locally induced trauma before and after treatment.

A survey will be completed by the users to assess usability of the V Needle.

After the first five (5) patients will be enrolled, and data through the last visit of the fifth patient is available, this data will be submitted to the FDA while study enrollment and visits continue. No Hemotek Medical V Needle treatments will occur until after FDA has reviewed the data from the first 5 patients and allows the study to proceed. Data will also be submitted to the FDA after the tenth patient completes their last visit and data is available. After the tenth patient, study enrollment and visits can continue, but no Hemotek Medical V Needle treatments will occur on the final 5-10 patients until the FDA allows the study to proceed. After FDA has found the data for the first 10 patients acceptable, the rest of the study can continue until the end.

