10.3 Statistical Analyses

10.3.1 Performance Endpoint Analysis

Although not a randomized study, each subject dialysis session will be performed using either the test needle or a control needle. The sites are instructed to perform 3 control sessions first and then 6 test sessions per enrolled subject, and in the case that a site deviates from this order, performance measure will be analyzed based on the needle used. Assuming there will be a 20% rate of attrition/drop-out, the remaining 18 subjects would contribute 108 test and 54 control sessions. Data will be pooled by session type (test vs. control) from all sites (no by-site analyses are planned).

The primary performance analysis will test the non-inferiority hypothesis as a difference of proportions between the test and control groups using a one-sided Farrington-Manning Score Test at a significance level of $\alpha=0.025$.

Additionally, the primary performance measure will be analyzed on the subject-level (utilizing a non-inferiority margin of 0.05) by testing the difference in mean success rates per subject across treatment groups using a one-sided paired t-test at a significance level of $\alpha=0.025$.

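### The question that decides success does not ask which needle the session was completed on, so a test session finished on another needle can score as a V Needle success

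*Combined protocol and SAP*

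**What the plan says.** Section 4.3 (and 1.17) gives the primary performance measure as "Percentage of successful hemodialysis sessions with the Hemotek device". Section 10.1.2 computes it as the "number of successful session completions of V Needle, as determined by the clinician, divided by the total number of sessions attempted".

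The same section then says how success is established. The clinician is asked "Was dialysis session incomplete because of a vascular access issue". A negative reply scores the session as a success; the section's explanation of such a reply is that "this indicates that the dialysis session completed successfully or was stopped for reasons that were not related to the vascular access".

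The only rule linking a session to a needle is in section 10.3.1. "Data will be pooled by session type (test vs. control) from all sites", and "in the case that a site deviates from this order, performance measure will be analyzed based on the needle used". The order in question is three control sessions followed by six test sessions.

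Section 5.1 adds: "All machine blood alarms, therapy interruptions, and/or partial or complete needle dislodgements will be recorded and immediately corrected". It does not say what the correction may be, or how it bears on success.

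**The concern.** The endpoint concerns sessions completed with the V Needle. The deciding question concerns whether the session was left incomplete for an access reason. The two agree when one needle is used throughout. They differ when the V Needle fails or cannot be inserted and the session is then completed on another needle. That session is not incomplete, so the answer is No and it scores as a success, although the V Needle did not complete it.

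Such an event is plausible. Section 3.3.1 names improper needle function and difficulty with cannulation among the risks specific to the V Needle. If such sessions are more common with the V Needle than with control needles, the observed difference moves towards non-inferiority by the size of the excess. The subject-level paired t-test uses the same success measure, so it offers no protection.

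**Working it through.** **The wording, applied to one case.** Take a test session in which the V Needle cannot be inserted or malfunctions and dialysis is completed on another needle.

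- Endpoint wording (4.3, and the rate in 10.1.2): not a completion with the V Needle, so a failure.
- Deciding question (10.1.2): the session was not incomplete, so the answer is No, a success.
- Needle-used rule (10.3.1): written for departures from session order. It says nothing about a change of needle within a session.

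The first two conflict and the third does not settle it.

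**Inputs for the arithmetic** (10.1.1, 10.3.1): success 98% for both needles, margin δ = 0.08, one-sided α = 0.025, Farrington-Manning score test, 2:1 sessions, 87 test sessions required, 108 test and 54 control planned. For 87 test sessions I take 44 controls (87/2 = 43.5, rounded up). Sessions are treated as independent, as the planned test does.

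Statistic: z = (p̂_T − p̂_C + δ) / √[p̃_T(1 − p̃_T)/n_T + p̃_C(1 − p̃_C)/n_C], where p̃_T and p̃_C are the maximum-likelihood estimates under p̃_C = p̃_T + δ. The test passes if z ≥ 1.960.

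**1. The plan's own figure.** Summing binomial probabilities over all passing outcomes at 98%/98% gives power 0.853 at 87/43 and 0.855 at 87/44, so the stated 85% reproduces. At 108/54 it is 0.913.

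**2. How many failures the test tolerates.** Example at 87/44 with 2 test and 0 control failures: p̂_T − p̂_C = 85/87 − 1 = −0.02299. The restricted estimates are 0.92 and 1.00, so the standard error is √(0.92 × 0.08/87) = 0.02909. Then z = (0.08 − 0.02299)/0.02909 = 1.9601 and p = 0.02499, a bare pass. With 3 test failures, z = (0.08 − 0.03448)/0.02909 = 1.565 and p = 0.059. In the same way:

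| Sessions | Control failures | Most test failures that pass (p) | One more (p) |
|---|---|---|---|
| 87/44 | 0 | 2 (0.02499) | 3 (0.059) |
| 87/44 | 1 | 3 (0.023) | 4 (0.051) |
| 108/54 | 0 | 3 (0.023) | 4 (0.050) |
| 108/54 | 1 | 4 (0.020) | 5 (0.042) |

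At 98% success the expected test failures are 87 × 0.02 = 1.7 and 108 × 0.02 = 2.2. Starting from 2 test failures, with 0 or 1 control failures, rescoring 1 or 2 test sessions reverses a pass at 87/44, and 2 or 3 at 108/54.

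**3. Illustration; the rates are assumptions.** Suppose both needles score 98% on the question as worded, and that the V Needle's 98% includes an excess of r percentage points finished on another needle. Scored as failures, these sessions give p_T = 0.98 − r against p_C = 0.98.

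| Excess r (points) | Pass probability, 87/44 | Pass probability, 108/54 |
|---|---|---|
| 0, or any r scored as worded | 85% | 91% |
| 2 | 50% | 56% |
| 4 | 22% | 24% |
| 6 | 8% | 8% |
| 8 | 2.8% | 2.3% |

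**4. Power if the stricter definition lowers success equally for both needles.** At 97%: 74% (87/44) and 81% (108/54). At 96%: 65% and 71%.

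**The case against.** The strongest reply is that section 10.1.2 should be read whole. It first speaks of completions with the V Needle, and a session finished on another needle is not one. That reading is reasonable and points to failure. But the section then names a single question as the means of deciding, and a clinician who answers it as worded reaches the opposite result.

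The triggering event is also inferred. No section describes replacing a needle; section 10.3.1 presumes one needle type per session; section 3.3.1 does not expect added risk; and the corrections in section 5.1 could be no more than resetting an alarm or re-taping. The Therapy Assessment Form is not in the documents and may define the terms. All of this stands and limits confidence. Needle faults would also be visible elsewhere, since alarms, dislodgements, ability to cannulate and device deficiencies are recorded (1.19, 1.23, 9.2.2). None of these enters the primary test, however.

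A reader might infer more than the documents support:

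- That the primary result will be biased in favour of the V Needle. The same question is put for control sessions, and no rate of replacement is given for either type.
- That the needle-used rule would turn such a session into a control success. The rule is confined to departures from session order.
- That the small failure counts measure this problem. They reflect a small test near 98% success; the wording matters because it decides how those few sessions are scored.
- That a pass obtained this way would be false. In the illustration, an excess below 8 points leaves the V Needle inside the margin, so a pass is easier but not wrong. At 8 points the V Needle is at the margin.

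**Conclusion.** The point holds as a conflict between the endpoint and the rule that scores it, and it should be fixed before data are scored. The size of any bias is unknown: it equals the excess of V Needle sessions finished on another needle, which the documents do not allow one to estimate. What can be shown is that one to three sessions could change the conclusion in the outcomes examined, and that the text gives no firm basis for scoring them. The session-level figures assume independence, although sessions are clustered within subjects. Confidence is medium, because replacement is inferred and the form has not been seen.

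**What to change.** In section 10.1.2 and on the Therapy Assessment Form, identically for both needle types:

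1. Add an item: was the session completed with the venous needle first attempted and, if not, why? Categories: could not be inserted; needle malfunction or performance; dislodgement, infiltration, movement or tape failure; other.
2. Score the session as a failure for the needle type first attempted if that needle could not be inserted or was replaced for malfunction or performance, even if the session was then completed.
3. State that such sessions stay in the group of the needle first attempted, so that the needle-used rule in 10.3.1 does not move them.
4. Add a sensitivity analysis that counts every replacement, whatever the reason, as a failure for both types. The study is unblinded (7.3) and the reason is a judgement, so the result should not rest on attribution alone. This also covers dislodgements that the device itself may have caused.

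Keep the present scoring of stops unrelated to the access.

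The cost is one form item, a short scoring rule and one extra analysis. Observed success may fall slightly below 98%, so the plan should say that the 85% power is conditional on 98% under this definition.
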